In response to the current COVID-19 epidemic, the following study processes will be carried out. To limit exposure to COVID-19 and ensure the safety, we will mostly use virtual options, such as video communications (zoom, Skype for business, or Microsoft team etc. depending on participants' convenience), REDCap, or phone. An exception will be given to participants who do not have computers or electronic devices; these individuals will visit Yale Stress Center for experimental procedure.

For the 4-week intervention, subjects will participate in the 4-week telehealth intervention (8 sessions, twice a week) for target intervention and subsequent smartphone app follow-up. During the 4-week period, the intervention group will visit Yale Stress Center twice a week for the PSB intervention. After the intervention, all participants will receive post-treatment assessment involving the examination of stress, mood, and alcohol use. The project will use prospective monitoring using smartphone app technology in the participants' natural environment during the 30 -days follow-up, during which we will monitor mood, stress, and alcohol intake daily. The intervention will be conducted via telehealth using Yale ITS approved video communications technology (e.g., Zoom, Skype for Business, or Microsoft Teams). After the 4-week intervention, all participants will undergo a post-intervention evaluation and followed for 30 days using a smartphone app. At the end of the 30-day survey period, they will have a remote session with a staff for post-study assessments and be remotely instructed on how to uninstall the app from their smartphone.

(a) Intake pre-intervention phases

Baseline Assessment (4-week intervention): Following screening using a Qualtrics prescreen survey or via phone, eligible subjects will be invited for a video session to obtain an informed eConsent (via REDcap) and an initial assessment to further determine eligibility via DSM-5 SCID interview. If the subject meets criteria, he/she will be scheduled for baseline sessions (2 hours each) to complete online assessments (via REDCap link) or in-person video interview. There will be 4-5 intake sessions depending on individual speed. All participants will work with specially trained research staff using standardized psychosocial assessments, self-report rating forms, and physical health questionnaires via remote sessions.

Assessments

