The COVID Stress Scales (CSS) (Taylor et al., 2020) is a 36-item designed to measure COVID-19 stress and anxiety symptoms including COVID danger and contamination fears, COVID fears about economic consequences, COVID xenophobia, COVID compulsive checking and reassurance seeking and COVID traumatic stress symptoms.

The Psychosocial Impact of COVID-19 (PIC) (Chung, 2020) is a 2-item assessing the level of difficulties and distress in people's lives over the past two weeks.

The Psychological Stress Associated with the COVID-19 Crisis questionnaire (PSACC) (M. Adamson, 2020) is a 37-item designed to measure the level of stress during the COVID-19 pandemic and characterize it according to location, gender, income, and other factor.

The UCLA Loneliness Scale (Version3) (Russell, 1996) is a 20-item measure that assesses how often a person feels disconnected from others.

The Interpersonal Support Evaluation List (ISEL) (Russell, 1996) is designed to measure perceptions of social support among individuals in the general population.

The COVID-19 Community Response Survey-Social Distancing Impacts (JHU-SDI) (Johns-Hopkins, 2020a) is designed to measure the impact of COVID-19 on people's lives due to a precautionary measure of social distancing.

The COVID-19 Community Response Survey-Substance Use (JHU-SU) (Johns-Hopkins, 2020b) is a 15-item designed to assess the use of substance after and during the COVID-19 pandemic.

(b) Target Intervention Combined with Breathing and Stress Management (PSB)

Subsequently, after the completion of the baseline assessment, all subjects will remotely participate in a 4-week digital intervention via video communications using platforms approved by Yale University IT services such as Zoom, Skype for Business, or Microsoft Teams. For 4 weeks, participants will attend 1.5 to 2 hours individual therapy sessions (8 sessions in total, twice a week) with [name] and her clinical team for prevention for alcohol use disorder using video communications. They will also be asked to use a smartphone app daily to assess treatment progress and learn coping skills (e.g., homework). At the end of the 4-week digital intervention, there will be post-treatment evaluations. Some components of the PSB intervention include:

- (1) Problem-focused target intervention partially adapted from cognitive behavioral therapy and NIAAA-approved coping skills training strategies (Kadden et al., 2003).

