B. What are the conditions or procedures for sharing of materials and/or distributing for future research projects? *Write here*

C. Is widespread sharing of materials planned? *Write here*

D. When and under what conditions will materials be stripped of all identifiers? *Write here*

E. Can donor-subjects withdraw their materials at any time, and/or withdraw the identifiers that connect them to their materials? *Write here*

- i. How will requests to withdraw materials be handled (e.g., material no longer identified: that is, anonymized) or material destroyed? *Write here*

F. Describe the provisions for protection of participant privacy *Write here*

G. Describe the methods for the security of storage and sharing of materials *Write here*

6. Subject Population: heavy/binge drinkers

7. Subject classification: Check off all classifications of subjects that will be specifically recruited for enrollment in the research project. Will subjects who may require additional safeguards or other considerations be enrolled

in the study? If so, identify the population of subjects requiring special safeguards and provide a justification for their involvement.

 Children	 Healthy	 Fetal material, placenta, or dead fetus
 Non-English Speaking	 Prisoners	 Economically disadvantaged persons
 Decisionally Impaired	 Employees	 Pregnant women and/or fetuses
 Yale Students	 Females of childbearing potential	

NOTE: Is this research proposal designed to enroll children who are wards of the state as potential subjects?

Yes No

8. Inclusion/Exclusion Criteria: What are the criteria used to determine subject inclusion or exclusion?

Inclusion Criteria:

- (1) Aged 18-55 years;
- (2) Ability to read and write English;
- (3) Heavy/Binge Drinkers: Drinking at levels to match heavy or binge drinking groups (NIAAA Clinician Guide, 2005): **Heavy Drinkers (HD):** Regular alcohol use over the past year of, at least 8 standard drinks/wk for women and at least 15 drinks/wk for men. **Binge Drinkers (BD):** Binge drinking patterns (Women: 4 or more drinks; men: 5 or more drinks in one setting).

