To test the efficacy of the PSB intervention in reducing stress, alcohol craving and use, all analyses will be conducted using the intent-to-treat sample and each hypothesis will be tested using General Linear models (GLMs) (Diggle, Heagerty, Liang, & Zeger, 2002) examining the main effects of Time (pre-/post-/Follow-up).

For smartphone data, alcohol use outcomes obtained from mobile app will be defined in both dichotomous and continuous manner (e.g., time to first drink or time to heavy drinking after the prevention; percent days abstinence and heavy drinking days (men: 5 or more; women: 4 or more) as continuous measures). Frequency, the total number of days of stress or alcohol use; and quantity, the average amount of alcohol use (number of drinks) or average levels of stress per occasion will also be computed. Multiple regression and mixed effects regression models (MRMs) will be used to evaluate the effects of prevention on prospective repeated assessments of stress, emotion, alcohol use, craving, and mood related data. Specific MRMs will model within person time varying and invariant data from daily stress and substance use patterns to assess group differences and examine whether behavioral changes after prevention predicts future stress and alcohol-related behaviors.

SECTION II: RESEARCH INVOLVING DRUGS, BIOLOGICS, RADIOTRACERS, PLACEBOS AND DEVICES

If this section (or one of its parts, A or B) is not applicable, check off N/A and delete the rest of the section.

A. RADIOTRACERS N/A

B. DRUGS/BIOLOGICS N/A

B. DEVICES N/A

SECTION III: RECRUITMENT/CONSENT AND ASSENT PROCEDURES

1. Targeted Enrollment: Give the number of subjects:

- Targeted for enrollment at Yale for this protocol: 100
- If this is a multi-site study, give the total number of subjects targeted across all sites: n/a

2. Indicate recruitment methods below. Attach copies of any recruitment materials that will be used.

 Flyers	 Internet/web postings	 Radio
 Posters	 Mass email solicitation	 Telephone
 Letter	 Departmental/Center website	 Television
 Medical record review*	 Departmental/Center research boards	 Newspaper

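### The supplementary app outcome frequency is a raw total of days with no allowance for unanswered daily surveys, so it falls with survey completion as well as with drinking or stress

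*Combined protocol and SAP*

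**What the plan says.** Section I, 13 lists the smartphone alcohol outcomes. It gives "time to first drink or time to heavy drinking after the prevention" as examples, and "percent days abstinence and heavy drinking days" as continuous measures. It then adds per-person summaries, the first being "Frequency, the total number of days of stress or alcohol use". Its companion, quantity, is averaged per occasion; frequency has no denominator. For modelling, "Multiple regression and mixed effects regression models (MRMs) will be used to evaluate the effects of prevention" on the repeated assessments, and the mixed models are also to "examine whether behavioral changes after prevention predicts future stress and alcohol-related behaviors". The section does not say which summary enters which model.

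The app asks for one questionnaire each evening (Section I, 4(c)). For the 30-day follow-up, Section I, 4 describes a period "during which we will monitor mood, stress, and alcohol intake daily". Monitoring also runs during treatment. Section I, 4(b) has participants "use a smartphone app daily to assess treatment progress and learn coping skills"; Section I, 2 and 3 describe daily monitoring alongside the 4-week intervention; and Section VI pays for 28 monitoring surveys separately from 28 intervention exercises. Section VI also pays follow-up bonuses for 14, 13 or 12 surveys answered out of 14, so some missed surveys are foreseen.

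**The concern.** A total over an incomplete diary mixes two things: how often the subject drank or felt stressed, and how often the subject answered. Two subjects with identical behaviour receive different totals if one answers fewer surveys. Because an unanswered day can only add zero, the total is never too high on this account, and it is too low whenever a missed day was a drinking or stress day.

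The direction matters because Section I, 4(b) gives the intervention to all subjects and Section I, 13 tests main effects of Time, so no defined parallel group would share the shortfall. If frequency is only described, post-treatment drinking and stress look lower than they were. If it enters the planned prediction models, differences in completion appear as differences in behaviour.

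**Working it through.** The documents give no completion rate, drinking rate or power figure for the app outcomes, so there is no stated figure to reproduce. The window lengths (28 and 30 days) and the tiers 13/14 and 12/14 come from Section VI. The 80% completion and all drinking rates below are assumptions.

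**Raw total.** Let c be the share of surveys answered and d the share of days with the behaviour. If missingness is unrelated to the behaviour, the expected total is 30 × d × c against a true 30 × d, so the relative shortfall is 1 − c whatever d is.

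| Completion | Shortfall | 6 true days | 12 true days | 18 true days |
|---|---|---|---|---|
| 13/14 | 7.1% | 5.6 | 11.1 | 16.7 |
| 12/14 | 14.3% | 5.1 | 10.3 | 15.4 |
| 80% | 20% | 4.8 | 9.6 | 14.4 |

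So two subjects who each drink on 12 of 30 days are expected to score 12.0 and 9.6 if one answers 30 surveys and the other 24. A subject drinking at the same 40% rate who stops reporting after day 15 scores 0.40 × 15 = 6.

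**Percent days abstinence.** With d = 0.40 (true value 60%) and c = 12/14, expected reported drinking days are 12 × 12/14 = 10.29.
- Unanswered days counted as abstinent: (30 − 10.29)/30 = 65.7%.
- Reported abstinent days over 30: 0.60 × 12/14 = 51.4%.
- Reported abstinent days over answered days: 60%.

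**Window length.** With complete data, a 30-day total exceeds a 28-day total at the same daily rate by 30/28 − 1 = 7.1%.

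**Limits of the answered-day rate.** Let r be the chance of missing a survey on a drinking day divided by that on a non-drinking day. Then P(miss | drinking) = r(1 − c)/(1 − d + r·d), which is also the shortfall of the total; the answered-day rate is the true rate times (1 − P(miss | drinking))/c. At c = 12/14:
- r = 2, d = 20%, 40%, 60%: totals are 23.8%, 20.4% and 17.9% low; answered-day rates are 11.1%, 7.1% and 4.2% low.
- r = 0.5, same d: answered-day rates are 7.4%, 6.2% and 4.8% high.

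**Time to heavy drinking.** Assume a constant daily chance h = 0.10 and c = 12/14. If missed days before the first recorded event count as event-free, the apparent daily chance is h × c = 0.0857. The median, ln 0.5/ln(1 − chance), becomes 7.7 days against a true 6.6. Censoring only at the last answered day does not remove this. The share with no heavy day by day 30 is (1 − h)^30: 4.2% at h = 0.10, 15.6% at 0.06 and 40.1% at 0.03. Infrequent heavy drinkers can be enrolled, since the criterion "Binge drinking patterns (Women: 4 or more drinks; men: 5 or more drinks in one setting" carries no minimum frequency.

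**The case against.** The strongest reply is that the plan adopts no wrong rule; it is silent. A reader might infer from the definition that a missed survey is to be scored as a day without drinking or stress. The documents do not say so. What stands is the arithmetic: a total computed as defined, on incomplete data, gives that day zero.

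A reader might also infer that falling completion between treatment and follow-up would be reported as improvement, or that the unequal windows distort the efficacy test. The plan states no comparison of app totals across the two windows, and does not say that frequency enters the Time analysis. The 7.1% window effect is therefore conditional on a comparison nobody has announced.

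On time to drinking, it is tempting to say that the plan applies linear regression to censored data. It assigns no model to those outcomes: the mixed models are for repeated assessments, which a single event time is not. The missing censoring rule and the missing denominator for percent days abstinence are details an analyst would ordinarily supply.

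Finally, there are mitigations: upload monitoring (Section I, 4(c)), completion bonuses (Section VI), and a Timeline Follow-Back covering alcohol during the study and follow-up (Section I, 4(a)). These reduce exposure or offer a second source. None is a scoring rule, the Timeline Follow-Back is not linked to the app outcomes, and it is not described as recording stress. The intent-to-treat statement says who is analysed, not how missed days count.

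**Conclusion.** The point stands as a minor one. As defined, frequency understates days of drinking or stress by one minus completion when missingness is unrelated to the outcome, and by more if drinking days are the ones missed. The size depends on completion, which the documents do not give; the gap in the definition does not. The denominator of percent days abstinence, the basis for heavy drinking days and the handling of time to heavy drinking should be settled with it, but they are secondary. These are supplementary outcomes. The planned day-level mixed models can work from the answered days, do not rely on the total, and are not criticised here. Nothing in the documents supports a claim that the main efficacy analysis is biased by this definition.

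**What to change.** - State how an unanswered survey is handled. Define frequency of stress days, frequency of alcohol days, percent days abstinence and heavy drinking days per answered day. Equivalent choices are a count model with log(answered days) as offset, or a mixed model for the daily yes/no records.
- Report answered days per subject beside each measure, separately for the treatment and follow-up windows.
- Because the answered-day rate is itself biased when drinking days are missed more or less often, add a sensitivity analysis that fills unanswered alcohol days from the Timeline Follow-Back. For stress days, give bounds with all or none of the unanswered days counted; their width is 1 − c, or 14.3 percentage points at 12/14.
- If time to heavy drinking is analysed, use a discrete-time hazard or Cox model, censoring subjects without an event at the last answered day. For missed days before the first recorded event, use the Timeline Follow-Back or treat the event time as interval-censored.

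The cost is a few sentences in the plan and modest programming on data already to be collected. The reported frequency will look slightly less favourable.
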